11.6 Iris Color

At screening, report iris color as blue, brown, gray, green, hazel, or other (with specification). All iris colors are desired to be enrolled, and the investigator's will not randomize, include or exclude subjects based on iris color.

11.7 Biomicroscopy

Biomicroscopic examination of the lids, conjunctiva, sclera, cornea, anterior chamber, iris and lens will be performed. Anterior chamber inflammation will be graded as follows:

Grade	0	1	2	3	4
Flare	Completely Absent	Barely Detectable	Moderate (iris and lens details clear)	Marked (iris and lens details hazy)	Intense (formed fibrin in aqueous)
Cells	No cells	1 to 5 cells	6 to 10 cells	11 to 20 cells	>20 cells

Examination of the anterior chamber for cells must be performed before either dilation or applanation tonometry. The light intensity of the slit lamp is to be turned to the maximum tolerated by the patient.

11.8 Intraocular Pressure

IOP will be measured by an MD or DO only, using a Goldmann applanation tonometer. Both eyes will be tested, with the right eye preceding the left eye. The operator will initially set the dial at 10 mmHg, then look through the slit lamp and adjust the dial to take the reading, and then record the results. The procedure will be repeated on the same eye twice consecutively. If the measurements are within 2 mmHg or less of each other, the mean of the 2 readings will be reported as the IOP at that time point. If the 2 readings are more than 2 mmHg apart from each other, a third (consecutive) reading will be taken and the median (middle) IOP will be reported as the IOP at that time point. Preferably, the same operator will measure IOP and the same tonometer will be used at each visit for a given patient.

11.9 Ophthalmoscopy

Ophthalmoscopy will be performed at the time points indicated in [Table 2](#), to examine the vitreous body, retina, and optic nerve head. Ophthalmoscopic assessments will be recorded

as normal or abnormal. Any abnormalities and pathologic findings will be graded as mild, moderate, or severe. The cup /disc ratio will be recorded horizontally and vertically for each examination, and reported in 0.1 increments.

Vitreous, Retina, Macula, Choroid: Assess for abnormalities in the retina, macula and choroid.

0 = Normal

1 = Abnormal

Optic Nerve: Assess for abnormalities in the optic nerve.

0 = Normal

1 = Abnormal

Cup/Disc Ratio: Assess the cup/disc vertical and horizontal ratio.

Optic Disc Hemorrhage:

0 = Absent

1 = Present

Rim Loss:

0 = Absent

1 = Present

Retinal Nerve Fiber Layer (RNFL) Defect:

0 = Absent

1 = Present

11.10 Gonioscopy

Gonioscopy should be performed after application of a topical anesthetic with a low level of illumination throughout that is consistent with standard clinical practice. If performed within 6 months (183 days) prior to screening and was documented in subject's records, no additional screening gonioscopy examination is necessary. Any observation of peripheral anterior synechiae should be noted. All four quadrants of the angle (superior, inferior, nasal, and temporal) should be evaluated using Shaffer's anterior chamber angle grading system:

Grade 4 (35°-45°): Ciliary body can be visualized.

Grade 3 (20°-35°): At least scleral spur can be identified.

Grade 2 (20°): Moderately narrow angle in which only the trabeculum can be identified.

Grade 1 (10°): Very narrow angle in which only the Schwalbe's line, and perhaps also the top of the trabeculum, can be identified.

Grade 0 (0°): Closed angle resulting from iridocorneal contact.

11.11 Pachymetry

Measurements of central corneal thickness will be performed for each participating subject, by using a calibrated ultrasonic pachymeter. It should be done after VA, refraction, and slit-lamp examination. Three measurements should be taken per eye with the subject in the sitting position and fixating on a target straight ahead. The probe should be removed from the cornea between measurements. All measurements from the right eye should be completed before taking any measurements from the left eye. The mean of the 3 recorded central corneal thickness measurements should be used to assess subject eligibility, as the mean will most likely reflect perpendicular placement of the pachymeter probe.

12 Methods and timing for assessing, recording, and analyzing safety parameters.

12.1 Adverse Event Reporting

12.1.1 Adverse Events

All observed or volunteered AEs regardless of treatment group or suspected causal relationship to the investigational product(s) will be reported as described in the following sections.

For all AEs, the investigator must pursue and obtain information adequate both to determine the outcome of the AE and to assess whether it meets the criteria for classification as a serious adverse event (SAE) requiring immediate notification to Sponsor or its designated representative. For all AEs, sufficient information should be obtained by the investigator to determine the causality of the AE. The investigator is required to assess causality. Follow-up by the investigator may be required until the event or its sequelae resolve or stabilize at a level acceptable to the investigator, and Sponsor concurs with that assessment.

Confidential

As part of ongoing safety reviews conducted by the sponsor, any non-serious AE that is determined by the sponsor to be serious will be reported by the sponsor as an SAE. To assist in the determination of case seriousness, further information may be requested from the investigator to provide clarity and understanding of the event in the context of the clinical study.

12.1.2 Reporting Period

For SAEs, the active reporting period to Sponsor or its designated representative begins from the time that the subject provides informed consent, which is obtained prior to the subjects participation in the study, eg, prior to undergoing any study-related procedure and/or receiving investigational product, through and including 30 calendar days after the last administration of the investigational product. SAEs occurring to a subject after the active reporting period has ended should be reported to the Designee/Sponsor if the investigator becomes aware of them; but will not be entered on a case report form; at a minimum, all SAEs that the investigator believes have at least a reasonable possibility of being related to investigational product are to be reported to the Designee/Sponsor.

12.1.3 Definition of an Adverse Event

Adverse Event is defined as any untoward medical occurrence in a subject participating in a clinical study which does not necessarily have a causal relationship with the study protocol or with the study treatment.

- Any unfavorable and unintended sign (including an abnormal laboratory finding), symptom, or disease with onset following the signing of informed consent through study exit, whether or not considered related to the study.
- An AE can also include a progression/worsening of underlying disease and hypersensitivity.
- Events occurring from drug overdose, whether accidental or intentional, events occurring from drug abuse, drug misuse, drug interactions, drug dependency, events occurring from drug withdrawal, and medication errors.

A Treatment Emergent Adverse Event (TEAE) will be defined as an AE with a start date on or after the first dose of study drug, or that worsened following first administration of study drug.

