To account for 10% attrition, approximately 624 subjects will be randomized in order to ensure that 560 subjects complete the 42 days (6 weeks) of dosing. Subjects who meet all inclusion/exclusion criteria will be randomized to receive the generic brinzolamide 1% suspension or brinzolamide 1% suspension (AZOPT®) using computer generated, blocked treatment assignments in a 1:1 ratio stratified by investigational site. Investigational product will be administered at approximately 8:00 AM, 4:00 PM and 10:00 PM in both eyes for 42 days, with exception of Visit 1 (Day 1) dose administered at only 4:00PM and 10:00PM. IOP assessments will be performed at approximately 8:00 AM and 10:00 AM on days 1 (baseline), 14, 21, and 42. IOP will be performed a second time (at approximately 10:00AM) on Days 1 (baseline), 14, 21, and 42. For subjects who discontinue the study before the end

of the treatment period, an Early Termination visit will be conducted within approximately one week after last study dose.

Figure 1 Study Design

[figure not shown]

Table 2 Study Design and Schedule of Assessments

Visit identifier	Screening	Visit 1	Visit 2	Visit 3	Visit 4	Early Termination
Visit Window	Day -42 to -4	Day 1	Day 14 ±4 days	Day 21 ±4 days	Day 42 ±4 days	Approximately within 7 days after last dose
Informed Consent	X					
Obtain Subject ID	X					
Randomization		X				
Inclusion/Exclusion criteria	X	X				
Demographics	X					
Medical History	X					
Prior and Concomitant medications	X	X	X	X	X	X
AE Monitoring	X	X	X	X	X	X
Check dosing diary			X	X	X	X
Collect unused investigational product				X	X	X
Collect dosing diary				X	X	X
BP and Pulse (sitting)	X	X	X	X	X	X
Visual Field Testing	X ^C					
Refraction	X	X*	X*	X*	X*	X*
BCVA	X	X	X	X	X	X
Biomicroscopy	X	X	X	X	X	X
Intraocular Pressure	X	X ^B	X ^B	X ^B	X ^B	X
Gonioscopy	X ^D					
Pachymetry	X					
Ophthalmoscopy	X	X	X	X	X	X
Urine Pregnancy Test	X	X			X	X
Dispense Investigational Product		X		X		
Dispense Dosing Diary		X		X		
Self-Administer Investigational Drug ^A			X ^A	X ^A	X ^A	

^A: indicates dosing will be self-administered at the site on visits 2, visit 3, and visit 4 after 8:00AM IOP measurement
^B: IOP measurement will occur twice (within ± 30 minutes of) 8:00AM and 10:00AM) at visit 1, visit 2, visit 3, and visit 4
^C: Visual Field testing to be conducted if no documentation within 6 months prior to screening
^D: Gonioscopy testing to be conducted if no documentation within 6 months prior to screening

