10.1.4 Administration

Administration instructions should be followed, which are on the investigational product label.

Each dose of investigational product (one eye drop) will contain 0.3 mg brinzolamide in either the generic brinzolamide 1% suspension or brinzolamide 1% suspension (AZOPT®).

One drop of investigational product should be instilled in each eye at approximately 8:00 AM, 4:00PM, and 10:00PM daily. On Day 1, the first day of dosing, only the 4pm and 10:00PM should be administered. On Day 42, the last day of dosing, only the 8:00AM dose is administered.

Subjects will self-administer investigational product daily on an outpatient basis; however, on Day 14, Day 21, and Day 42 the 8:00AM dose will be self-administered at the investigational site, following the 8:00AM IOP. The dose must be self-administered in a secluded room without any investigational site staff present within 30 minutes of 8:00 AM. Investigational site staff must not be in the room whenever the treatment is taken out of the masked external packaging or the subject is dosed with investigational product.

Subject knowledge and understanding of the dosing requirements must be verified before the subject leaves the investigator site at each visit.

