11.1.2 Visit 1 (Day 1)

Subjects must continue to satisfy all inclusion/exclusion criteria in order to be eligible for randomization.

The following procedures will be completed:

- Re-check inclusion/exclusion criteria (only those eligibility criteria that apply at Day 1);
- Review prior/concomitant treatments;
- Blood pressure/pulse rate (sitting);
- Best corrected visual acuity;

NOTE: Refraction must be performed if a decrease in VA of two or more lines from the previous assessment occurs.

- Biomicroscopy
- IOP at 8:00 AM \pm 30 minutes and 10:00 AM \pm 30 minutes;
- Ophthalmoscopy
- Assess and record adverse events (AEs);
- Urine hCG for all females of childbearing potential;
- Randomize the subject to a treatment group;

- To prepare for study participation, subjects will be instructed on the use of Concomitant Medications ([Section 9.3](#));
- Dispense dosing diary and instruct subject on completion;
- Dispense investigational product in masked external packaging and instruct subject on self-administration, storage, and return.
- First dose will be self-administered at 4pm, then followed by 10pm dose.

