11.4 Best Corrected Visual Acuity

Preferably, the same visual acuity examiner should perform each best corrected visual acuity measurement for a given subject. Best corrected visual acuity (BCVA) will be assessed using an Early Treatment Diabetic Retinopathy Study (ETDRS) eye chart (placed at 13 feet or 4 meters) or equivalent eye chart. BCVA should be performed prior to any exam requiring contact with the eye or drops to dilate or anesthetize the eye. If most of the letters are read on a line, then that line will be counted. For example, if the patient reads 20/25 +3, 20/20 will be recorded. Only the nearest Snellen line will be reported without plus and minus letters.

A decrease in BCVA of 3 lines or more from the screening visit will be reported as an adverse event. If visual acuity at screening is better than 20/20, any decrease in visual acuity will be calculated from 20/20.

The BCVA will be assessed at all visits as indicated in the Schedule of Activities.

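### The treatment-emergent definition works by start date, so an adverse event that begins on Day 1 before the 4 PM first dose is labelled treatment-emergent

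*Combined protocol and SAP*

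**What the plan says.** Section 12.1.3 gives the TEAE definition two limbs. The first is "an AE with a start date on or after the first dose of study drug". The second is "or that worsened following first administration of study drug". The same section collects AEs from consent, covering any sign, symptom or "disease with onset following the signing of informed consent through study exit", so events before dosing are AEs in this trial.

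Dosing starts late on Day 1. Section 10.1.4 says: "On Day 1, the first day of dosing, only the 4pm and 10:00PM should be administered". Section 11.1.2 agrees: "First dose will be self-administered at 4pm, then followed by 10pm dose".

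The clinic work on that day is done in the morning. Section 7.1 says: "IOP assessments will be performed at approximately 8:00 AM and 10:00 AM on days 1 (baseline), 14, 21, and 42". Section 11.1.2 also lists blood pressure and pulse, visual acuity, biomicroscopy, ophthalmoscopy and the recording of AEs, followed by randomization and dispensing.

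Two rules can create an AE at that visit because they use screening as the reference. Section 11.4 says: "A decrease in BCVA of 3 lines or more from the screening visit will be reported as an adverse event". Section 11.2 does the same for a blood pressure or pulse change that the investigator judges clinically significant.

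Section 13.3 describes the AE summaries, including the Tier-2 and Tier-3 tables. It refers to AEs throughout and does not use the term TEAE.

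**The concern.** A TEAE table is meant to hold events that could have been caused by study drug. A rule that compares calendar dates cannot separate the morning of Day 1 from the evening. In many trials this hardly matters, because the first dose is given at the baseline visit. Here a complete ophthalmic examination and a scheduled AE assessment come hours before the first drop, on the same date, for every subject.

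Comparing the safety and tolerability of the two products is the only secondary objective. Events that began before exposure say nothing about that comparison. Including them adds non-informative counts to both arms in any TEAE incidence table.

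**Working it through.** The plan gives no figure on this point, so there is nothing to reproduce. The check is a comparison of rules, followed by a scale calculation on assumed rates.

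**1. Gap between the Day 1 assessments and the first dose.** Section 11.1.2 sets the IOP readings at 8:00 and 10:00 AM, each ± 30 minutes, and the first dose at 4 PM (16:00).
- 8:00 reading: 16 − 8.5 = 7.5 h to 16 − 7.5 = 8.5 h before dosing.
- 10:00 reading: 16 − 10.5 = 5.5 h to 16 − 9.5 = 6.5 h before dosing.

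**2. The rule applied to three onsets.**

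| Onset | By date | By date and time |
|---|---|---|
| Day before Day 1, 09:00 | not a TEAE | not a TEAE |
| Day 1, 09:00 | TEAE | not a TEAE, unless it worsens after dosing |
| Day 1, 17:00 | TEAE | TEAE |

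Only the middle row changes.

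**3. Which records fall in the middle row.** Ocular irritation that starts after the 10:00 tonometry on Day 1 does. A three-line visual acuity loss first seen at Visit 1 does only if it is dated to Day 1. Screening lies 4 to 42 days earlier (section 11.1.1), so the loss may be dated to that interval, and it is then not a TEAE unless it worsens after dosing.

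**4. Scale.** The documents give no rate of Day 1 pre-dose AEs. As an assumption, let a proportion p of subjects have one. With 312 randomized per arm (section 13.1), the number per arm is 312 × p:
- p = 0.5%: 1.56 per arm, 3.12 in total
- p = 1%: 3.12 per arm, 6.24 in total
- p = 2%: 6.24 per arm, 12.48 in total

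**5. Effect on the planned statistic.** Section 13.3 reports Tier-2 events as a risk difference with a 95% CI. Suppose a term has post-dose rates q1 and q2 in the two arms, with pre-dose events independent and equally frequent in each. The counted rate is r = 1 − (1 − q)(1 − p), so the difference becomes (q2 − q1)(1 − p). For illustrative rates of 2% and 4%:
- p = 0: 2.00 percentage points
- p = 0.5%: 2.00 × 0.995 = 1.99
- p = 1%: 2.00 × 0.99 = 1.98
- p = 2%: 2.00 × 0.98 = 1.96

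The point estimate hardly moves. The interval widens somewhat. Its half-width is 1.96 × √{[r1(1 − r1) + r2(1 − r2)]/312}, using the simple normal interval because the plan names no method. At p = 0 this is 1.96 × √(0.0580/312) = 2.67 points. At p = 2%, where r1 = 3.96% and r2 = 5.92%, it is 1.96 × √(0.0937/312) = 3.40 points.

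**The case against.** The strongest reply is that the definition is ambiguous rather than wrong. It sets the start date against the first dose, not against the date of the first dose, and its second limb speaks of the first administration. A reader could apply it by clock time. Section 13 also defers detailed methods to a SAP, and the text reviewed contains no separate SAP or CRF; either might record onset times or settle same-day events. This stands in part: it limits the point to the text as written. That text supplies nothing with which to apply a time-based reading.

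It can also be said that counting same-day events is a cautious default. For an event of unknown time that is fair, and the fix keeps it. It is not a reason to count an event already on record from the morning clinic.

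A third reply is that the definition is not tied to any named table. Section 13.3 classifies AEs, and section 6.4 frames the endpoint as treatment-related AEs, which rests on the causality assessment. This stands in full and shapes both the verdict and the fix.

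A reader might go further and infer that pre-dose events will push Preferred Terms over the 5% Tier-2 line, which is 16 subjects of 312 (0.05 × 312 = 15.6, rounded up). The documents do not support this. Taken literally, section 13.3 counts any reported AE, so such events would count toward the line whether or not section 12.1.3 is reworded. The pre-dose rates needed to estimate a crossing probability appear nowhere.

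**Conclusion.** The point holds as a minor defect of definition. Applied by date, section 12.1.3 labels an AE that starts on Day 1 before the 4 PM dose as treatment-emergent although no drug had been taken. The consequence is a few non-informative events in any TEAE incidence table: about 1.6 to 6.2 subjects per arm if 0.5% to 2% of subjects are affected. That range is assumed, and the documents cannot confirm or narrow it.

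No between-arm bias is expected. Section 11.1.2 lists the clinic assessments before randomization, and nobody has taken drug until 4 PM. The primary IOP analysis is unaffected, and the planned risk difference is essentially unchanged.

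A reader might infer that the misclassification makes the two products look materially more alike. A ratio of incidences would shrink, from 2.0 to about 1.5 in the 2% against 4% illustration at p = 2% (5.92/3.96), but the plan reports no such ratio. The risk difference it does report moves only from 2.00 to 1.96 points.

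**What to change.** In section 12.1.3, define a TEAE as an AE with onset after the date and time of the first dose, or one that worsened after it. Add two conventions:
- AEs first recorded at the Visit 1 clinic assessments are pre-treatment unless they worsen after dosing.
- Any other Day 1 AE with unknown onset time counts as treatment-emergent.

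In section 13.3, state that the AE summaries and the Tier-2 and Tier-3 tables use TEAEs so defined. Without that sentence the revised definition reaches no named analysis. If a SAP is still to be finalized, it should carry the same wording, settled before unmasking.

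The visit of recording is enough to classify AEs noted at the Visit 1 clinic. For other AEs that start on Day 1, a single field for before or after the first dose is the most that is needed. The remaining downside is occasional misclassification when the time is wrongly recorded; the default for unknown times errs toward counting the event.

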12.2 Serious Adverse Events

A serious adverse event is any untoward medical occurrence at any dose that:

- Results in death;
- Is life-threatening (immediate risk of death);
- Requires inpatient hospitalization or prolongation of existing hospitalization;
- Results in persistent or significant disability/incapacity (substantial disruption of the ability to conduct normal life functions);
- Results in congenital anomaly/birth defect.

Medical and scientific judgment is exercised in determining whether an event is an important medical event. An important medical event may not be immediately life-threatening and/or result in death or hospitalization. However, if it is determined that the event may jeopardize the subject, or may require intervention to prevent one of the other AE outcomes, the important medical event should be reported as serious.

Examples of such events are intensive treatment in an emergency room or at home for allergic bronchospasm; blood dyscrasias or convulsions that do not result in hospitalization; or development of drug dependency or drug abuse.

A serious injury that can cause a serious deterioration in state of health can include:

- a life-threatening illness, even if temporary in nature;
- a permanent impairment of a body function or permanent damage to a body structure;
- a condition necessitating medical or surgical intervention to prevent the above 2 bulleted items

- Examples: clinically relevant increase in the duration of a surgical procedure; a condition that requires hospitalization or significant prolongation of existing hospitalization;
- any indirect harm as a consequence of an incorrect diagnostic or in vitro diagnostic device test results when used within the manufacturer's instructions for use;
- fetal distress, fetal death, or any congenital abnormality or birth defects.

All SAEs, whether related or unrelated to study drug, must be immediately reported to the designee within 24 hours of the investigator's awareness of the event. All SAEs must be reported via confirmed email/facsimile transmission and must be submitted on a written SAE report form signed by the investigator within 24 hours of the investigator's awareness of the event.

- The fax number for reporting an SAE is:

- [REDACTED]
- [REDACTED]
- [REDACTED]
- [REDACTED]

Investigators should not wait to receive additional information to fully document the event before notifying Medical Monitor of an SAE. If only limited information is initially available, follow-up reports are required. Additional relevant information such as hospital records and autopsy reports should be provided to designee as soon as they are available. Should the investigator become aware of an SAE (regardless of its relationship to investigational product) that occurs within 30 days after stopping the study drug, the SAE must be reported in accordance with procedures specified in this protocol.

The investigator should take all appropriate measures to ensure the safety of the subjects, notably he/she should follow a subject with an SAE until the event has resolved or the condition has stabilized. This may imply that follow-up will continue after the subject has left the study, and that additional investigations may be requested by the sponsor.

The Designee will review forms and documents for completeness and forward to Sponsor within 24hrs of receipt via email: [REDACTED]

